#### **2.5.3 Handling of remaining intercurrent events of primary estimand**

The primary analysis will account for different intercurrent events as explained in the following:

##### **Systemic corticosteroid dose increase and/or iv corticosteroid use before Week 8 for any reason**

Composite variable strategy is applied to this intercurrent event. If a participant had corticosteroid dose increase and/or iv corticosteroid use during the first 8 weeks after study treatment start, he/she will be considered as non-responder at Week 8 regardless of whether adapted ACR 30 assessment is available (non-responder imputation).

## **Discontinuation of study treatment before Week 8 for any reason**

Treatment policy strategy is applied to this intercurrent event. When a participant discontinued study treatment before Week 8, but adapted ACR 30 assessment at Week 8 is available, it will be included in the analysis.

### **2.5.4 Handling of missing values/censoring/discontinuations**

Missing adapted ACR 30 assessment at Week 8 will be imputed with non-responder regardless of the reason for missing data (non-responder imputation).

### **2.5.5 Supplementary analyses**

All of the supplementary analyses defined below will be based on the FAS.

The supplementary clinical question of interest is: What is the benefit of Canakinumab in Japanese AOSD patients to improve systemic and articular manifestation of AOSD regardless of systemic corticosteroid dose increase and/or intravenous administration of corticosteroid and regardless of treatment discontinuations for any reason? In this supplementary estimand, the population, primary variable and summary measure will be the same as the primary estimand, but the intercurrent event of corticosteroid dose increase and/or intravenous administration of corticosteroid will be ignored following a treatment policy strategy. The supplementary estimand will capture the effect of canakinumab regardless of increase in systemic corticosteroid dose and intravenous administration of steroid, reflecting possibly the situation under clinical practice.

The primary analysis will be repeated for the supplementary estimand without handling of systemic corticosteroid dose increase and/or iv corticosteroid use before Week 8 for any reason described in [Section 2.5.3.](#), i.e. even when a participant had these events, adapted ACR 30 assessment at Week 8 will be included as observed. Hypothesis testing will not be performed.

### **2.5.6 Supportive analyses**

The primary analysis will be repeated, using data from all 14 participants, based on the FAS at the timing of the Week 28 interim analysis. Hypothesis testing will not be performed.

## **2.6 Analysis of the key secondary objective**

### **2.6.1 Key secondary endpoint**

The secondary clinical question of interest is: What is the effect of Canakinumab on oral corticosteroids tapering in Japanese AOSD participants after Week 8 up to Week 28?

The justification for the secondary estimand is that it will capture the ability of canakinumab on corticosteroid tapering based on the success criteria starting from Week 8 up to Week 28 after canakinumab administration.

The secondary estimand is described by the following attributes:

1. Population: Japanese AOSD participants who use systemic corticosteroid at baseline and are administered canakinumab at Week 8.

2. Endpoint: Successful oral corticosteroids tapering by Week 28. Participants will be considered as being able to taper oral corticosteroid according to pre-defined criteria depending on baseline dose.
3. Treatment of interest: canakinumab 4mg/kg.

The analysis will account for different intercurrent events as explained in the following:

1. Discontinuation of study treatment after Week 8 for any reason: If a participant early discontinued study treatment after Week 8 but had the Week 28 assessment regarding corticosteroid tapering, he/she will be included in the analysis.
2. Intravenous administration of steroid at any time between Week 8 and Week 28: If a participant had intravenous administration of steroid at any time between Week 8 and Week 28 assessment visit (i.e. between Week 8 visit and Week 28 visit), he/she will be considered as corticosteroid tapering failure at Week 28 regardless of whether the corticosteroid data is available (non-responder imputation)

The summary measure: proportion of participants who are able to taper oral corticosteroids successfully at Week 28.

## **2.6.2 Statistical hypothesis, model, and method of analysis**

Frequency table with the number and percentage of participants who were able to taper oral corticosteroids successfully at Week 28 will be provided for the participants in the FAS who used systemic corticosteroid at baseline and were administered study treatment at Week 8, i.e. the number of evaluable participants could be smaller than the number of participants in the FAS. Participants who were able to taper oral corticosteroids successfully at Week 28 will be classified as “Tapered” or “Steroid free”, and “Steroid free” is defined as participants that did not use the steroid in the last point of time.

This analysis will also be performed by the subgroups described in Section 2.2.1.

## **2.6.3 Handling of missing values/censoring/discontinuations**

If the successful tapering of corticosteroids can not be derived due to missing information, it will be imputed with the last available data from Week 8 to Week 28 (last observation carried forward (LOCF) approach).

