9.1 Discontinuation from study treatment and from study

9.1.1 Discontinuation from study treatment

Discontinuation of study treatment for a participant occurs when study treatment is permanently stopped for any reason (prior to the planned completion of study treatment administration, if any) and can be initiated by either the participant or the investigator.

The investigator must discontinue study treatment for a given participant if, he/she believes that continuation would negatively impact the participant's well-being.

Discontinuation from study treatment is required under the following circumstances:

- Participant/guardian decision
- Pregnancy
- Use of prohibited treatment as per recommendations in the prohibited treatment section
- Any situation in which continued study participation might result in a safety risk to the participant
- Any severe or serious adverse event that is not compatible with administration of study medication, including adverse events that require treatment with an unacceptable co-medication
- Onset of malignancy
- Occurrence of uncontrolled life-threatening infection
- Any other protocol deviation that results in a significant risk to the participant's safety

The investigator should consider discontinuing participants from study treatment who experience a clinically important worsening of disease activity compared to baseline at two consecutive visits after Week 4. A clinically important worsening will be defined as participants who do not meet the adapted ACR30 criteria by Week 12 or participants with non-response (defined as Adapted ACR <30) at two consecutive visits at any time in the study beginning at Week 12.

All participants who discontinue will complete an EOS visit, be discontinued from the trial and be treated as per standard local medical practice (see also [Section 10.1.3](#) for information on SAE reporting following the last dose of study medication).

If discontinuation from study treatment occurs, the investigator should make a reasonable effort to understand the primary reason for the participant's discontinuation from study treatment and record this information.

Participants who discontinue from study treatment agree to return for the end of treatment and follow-up visits indicated in the Assessment Schedule (refer to Section 8).

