12.5 Analysis supporting secondary objectives

12.5.1 Key efficacy endpoint

The secondary estimand is the effect of canakinumab on oral corticosteroids tapering starting from Week 8 to Week 28. Successful tapering of corticosteroids will be derived on prednisone equivalent dose per day (mg/kg/day) as described in [Section 8.3.2](#). Further details will be described in the statistical analysis plan.

Frequency table with the number and percentage of participants who were able to taper oral corticosteroids successfully at Week 28 will be provided for the FAS. The participants who used systemic corticosteroid at baseline and were administered study treatment at Week 8 will be considered in this analysis.

The analysis will account for different intercurrent events as explained in the following:

1. Discontinuation of study treatment after Week 8 for any reason: If a participant early discontinued study treatment after Week 8 but had the Week 28 assessment regarding corticosteroid tapering, he/she will be included in the analysis.
2. Intravenous administration of steroid at any time between Week 8 and Week 28: If a participant had intravenous administration of steroid at any time between Week 8 and Week 28, he/she will be considered as corticosteroid tapering failure (non-responder imputation)

If the successful tapering of corticosteroids cannot be derived due to missing body weight, it will be imputed with the last available data from Week 8 to Week 28 (last observation carried forward (LOCF) approach).

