### 3 Sample size calculation

### 4 Change to protocol specified analyses

NA

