## 5.6 Documentation of statistical methods

### 5.6.1 Calculation of prednisone equivalent dose (mg/kg/day) of oral steroids

The oral steroid dose at baseline will be the measurement on the date of baseline (Day 1) recorded on the concomitant medication page in eCRF. The oral steroid used for AOSD indication will be used. The oral steroid dose will be converted to prednisone equivalent dose using the conversion factor in [Table 5-2](#). The prednisolone equivalent dose will be derived by dividing the dose of the oral steroid dose by the corresponding conversion factor. Body weight will be the measurement at baseline (Day 1) or the last available weight before baseline.

The oral steroid dose at post-baseline assessment visits after Week 8 will be the measurement on one day before the date of corresponding assessment visits. Body weight will be the last available measurement on or before the date of steroid dose measurement.

The daily dose will be calculated by multiplying the conversion factors corresponding to the frequency recorded in eCRF (see [Table 5-3](#)). If participants use more than 2 oral steroids for AOSD on the same day, total dose per day will be used.

When a participant continued the study, if there is no concomitant oral steroid data at the assessment day, it will be considered as steroid free (0 mg).

If the oral steroid data is available but with missing information (e.g., body weight, frequency), the prednisone equivalent dose will be set to missing.

For example, if a participant weighs  $w$  kg and is taking  $x$  mg of Betamethasone 2 times per day and  $y$  mg of Hydrocortisone 3 times per day, the prednisone equivalent dose will be calculated as follows:

Prednisone equivalent dose per day =  $(x/0.12*2 + y/4*3)/w$ .

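### SAP 2.6.3 widens LOCF for the Week 28 steroid-tapering endpoint from missing body weight to any missing information, and SAP Section 4 does not declare the change

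*SAP*

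**What the plan says.** **Protocol 12.5.1** gives one missing-data rule for the key secondary endpoint: "If the successful tapering of corticosteroids cannot be derived due to missing body weight, it will be imputed with the last available data", using data from Week 8 to Week 28. Whether the weight or the tapering status is carried, the trigger is missing weight alone.

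**SAP 2.6.3** gives the corresponding rule: "If the successful tapering of corticosteroids can not be derived due to missing information, it will be imputed with the last available data", over the same weeks. It is the only rule in that section, whose heading covers missing values, censoring and discontinuations.

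**SAP Section 4**, titled "Change to protocol specified analyses", contains only NA.

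Other provisions bear on the rule:
- Success requires a dose criterion and at least adapted ACR30 (Protocol 8.3.2, SAP 1.2).
- Intravenous steroid between Week 8 and Week 28 makes the participant a failure whatever else is recorded (SAP 2.6.1).
- A participant who stopped treatment but has a Week 28 tapering assessment is included (Protocol 12.5.1, SAP 2.6.1). Neither document has a separate rule for one who has no such assessment.
- Protocol 9.1.1 says: "All participants who discontinue will complete an EOS visit, be discontinued from the trial and be treated as per standard local medical practice".
- An early leaver's EOS visit is mapped to a scheduled visit (SAP 2.1.2, Table 2-1, and 2.14).
- SAP 5.6.1 says: "If the oral steroid data is available but with missing information (e.g., body weight, frequency), the prednisone equivalent dose will be set to missing".
- A missing primary endpoint is imputed as non-response (SAP 2.5.4).

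**The concern.** The endpoint asks whether a lower steroid dose can be held to Week 28 with ACR30 maintained. A participant who tapers early, leaves, and has no Week 28 status has not shown that. Under the SAP wording, such a participant can still be scored a success on the strength of an earlier visit. The primary endpoint treats the comparable gap as non-response.

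The trial has no control arm and at most 14 participants, and the Week 28 analysis supports the registration dossier. One or two participants scored this way would visibly change the reported proportion. Because Section 4 says NA, a reader of the study report would not know that the rule differs from the protocol.

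**Working it through.** The documents give no expected rate for this endpoint, and the sample size text is redacted, so there is no stated figure to reproduce. The check is a comparison of texts followed by simple arithmetic.

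**1. What the SAP rule adds.** The protocol trigger is missing body weight. SAP 5.6.1 already takes the last available weight on or before the dose date, so a missing weight should seldom arise after baseline. In practice SAP 2.6.3 acts mainly on other items. These are a steroid frequency recorded as unknown or other (set to missing in Table 5-3), a missing ACR30, or no Week 28 visit.

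**2. Who can be carried as a success.** An EOS visit on Days 173 to 200 maps to Week 28 and supplies its own value. LOCF therefore matters for those whose EOS visit falls before Day 173, or who lack a usable EOS assessment. The carried status is success only if the last available visit met the dose criterion and ACR30, with no intravenous steroid from Week 8 on. Post-baseline dose is read one day before the visit (SAP 5.6.1), so an oral increase made at the exit visit is not in the last dose.

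**3. How early success can be reached.** Inputs are the guideline rate of 0.1 mg/kg per week (Protocol Table 6-2), a first step at Week 8, no pause, and the thresholds in Protocol 8.3.2. Steps fall on Days 57, 64, 71 and 78, so four are complete before the Day 84 reading for the Week 12 visit (Day 85).

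| Baseline (mg/kg/day) | Dose that qualifies | Steps needed | First visit showing it |
|---|---|---|---|
| 0.3 | 0.2 | 1 | Week 12 |
| 0.5 | 0.2 | 3 | Week 12 |
| 0.8 | 0.5 | 3 | Week 12 |
| 0.9 | 0.5 | 4 | Week 12 |
| 1.0 | 0.5 | 5 | Week 16 |

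A success could thus be carried for 28 − 12 = 16 weeks, or 28 − 16 = 12 weeks from the highest baseline dose.

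**4. Effect on the proportion.** If k leavers are carried as successes among N evaluable participants, LOCF exceeds failure imputation by k/N.

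| k | N = 11 | N = 14 |
|---|---|---|
| 1 | 9.1 points | 7.1 points |
| 2 | 18.2 points | 14.3 points |
| 3 | 27.3 points | 21.4 points |

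N is an upper limit in each column, because SAP 2.6.2 notes that "the number of evaluable participants could be smaller than the number of participants in the FAS". With a smaller N the shift per participant is larger.

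**5. Illustration (all counts assumed).** Nine participants are evaluable. Five succeed at Week 28, two fail at Week 28, and two leave at Week 16.
- LOCF, both leavers last seen as successes: 7/9 = 78%.
- LOCF, both leavers without ACR30 at EOS: 5/9 = 56%.
- Missing Week 28 status counted as failure: 5/9 = 56%.
- Leavers excluded: 5/7 = 71%.

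LOCF alone therefore accounts for at most 78% versus 56% here, and for nothing if the EOS visits record the relapse.

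**The case against.** **The EOS visit protects the endpoint.** Discontinuers complete an EOS visit at which adapted ACR is assessed, and that visit can be the last available observation. This stands. A reader might infer that everyone who leaves after an early taper becomes a Week 28 success. The documents do not support that: loss of ACR30 at EOS, or intravenous steroid, gives failure. What remains is the leaver who still qualifies at the last visit, or whose exit assessment is missing or incomplete.

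**A narrower reading is available.** SAP 5.6.1 uses the same term for gaps in an existing steroid record, with weight and frequency as examples. The heading of 2.6.3 is also generic and recurs elsewhere in the SAP. The text does not settle which reading applies. The narrow one does not remove the mismatch, because the examples are not exhaustive and frequency already goes beyond the protocol.

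**The direction of bias depends on the comparator.** LOCF cannot give a lower proportion than counting missing status as failure. Compared with excluding leavers it can be lower, as 56% versus 71% shows. This stands.

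**Week 28 data may exist after discontinuation.** Protocol 9.1.1 says discontinuers leave the trial at EOS, but it also says they return for follow-up visits, as does Protocol Section 8. These statements need reconciling. How many participants will lack a Week 28 assessment is unknown.

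**The denominator follows the protocol.** If two further baseline steroid users stopped before Week 8, the illustration could be pushed to 5/11 = 45%. A reader might take that as the size of the LOCF problem. It is not, because it also changes the denominator. Restriction to those dosed at Week 8 is the estimand population in Protocol 2.2, which the SAP repeats.

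**The endpoint is descriptive.** It has a frequency table and no test. SAP 2.14 also tabulates tapering success by visit for the first 11 participants, so some of the effect would be visible. This lowers the severity.

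**Conclusion.** The discrepancy is established from the text: the SAP broadens the LOCF trigger and declares no departure from the protocol. Its consequence is conditional. Read literally, the rule can score a leaver as a Week 28 success, at 9.1 points per participant (N = 11) or 7.1 points (N = 14) relative to failure imputation. The 16-week carry assumes the fastest guideline taper. Protocol 6.2.1.1 makes tapering depend on the investigator's judgment and requires a pause of at least two weeks after worsening, so actual intervals may be shorter. The number of leavers is an assumption throughout.

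Severity is moderate: an undeclared and potentially favourable rule on the key secondary endpoint of a very small single-arm trial, with no effect on type I error.

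A reader might also infer that the rule was widened with results in view. The trial is open-label, SAP 2.14 dates the first 11 participants' Week 28 milestone to 6 December 2022, and the SAP cites the protocol of 19 May 2023. The SAP's document history is redacted, so the documents do not support that inference.

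**What to change.** In SAP 2.6.3:
1. Limit LOCF to missing body weight, as in Protocol 12.5.1.
2. State that a participant in the estimand population whose Week 28 dose or adapted ACR30 status is missing for another reason, for example after discontinuation, counts as a tapering failure, in line with the primary endpoint.
3. Keep the wider LOCF rule as a labelled sensitivity analysis.

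In SAP Section 4, replace NA with an entry for item 2 and any other departure. Item 2 is a new rule and not a restoration, because the protocol is silent on a missing Week 28 status. Returning to the protocol wording alone would leave the gap open.

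A table over all baseline steroid users, with those not dosed at Week 8 counted as failures, is an optional supplement and not a correction.

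The cost is a few lines of SAP text and one sensitivity table. The downside is that the reported success rate may be lower, and failure imputation will count against the drug any leaver who had in fact held the lower dose.

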## **2.7 Analysis of secondary efficacy objective(s)**

### **2.7.1 Secondary endpoints**

The secondary efficacy endpoints of this study are Adapted ACR 30/50/70/90/100 response criteria, components of adapted ACR criteria, corticosteroid dose tapering, rash, DAS28-CRP, systemic feature score, and total IL-1 $\beta$  level.

## **2.7.2 Statistical hypothesis, model, and method of analysis**

All efficacy endpoints will be summarized using the FAS. All analyses for secondary endpoints will be basically performed using data from all 14 participants based on the FAS. The analyses that will be performed based on the data up to the time when the first 11 participants in the FAS is described in Section 2.14.

### **Adapted ACR 30/50/70/90/100 response criteria**

The adapted ACR 30/50/70/90/100 at Week 8 and the adapted ACR 30/50/70/90/100 at each visit including Week 8 will be analyzed separately.

For the adapted ACR 50/70/90/100 at Week 8, the primary analysis will be repeated as performed for adapted ACR 30 except the statistical hypothesis testing. The results will be presented with the primary analysis of the adapted ACR 30. In addition, the adapted ACR 30/50/70/90/100 response at Week 8 will be summarized with the number and percentage of participants by the subgroups described in Section 2.2.1.

For the adapted ACR 30/50/70/90/100 at each visit, frequency tables with the number and percentage of participants achieving the adapted ACR 30/50/70/90/100 criteria will be provided by scheduled visit.

The line plot of the percentage of participants achieving the adapted ACR 30/50/70/90/100 response for each visit will be provided.

### **Components of adapted ACR criteria**

For the adapted ACR individual components from 1 to 5, summary statistics for the observed values and the change/percent change from baseline will be provided by scheduled visit. For absence of intermittent fever in the preceding week, frequency tables with the number and percentage of participants with or without intermittent fever will be provided by scheduled visit.

The 6 adapted ACR individual components are defined as follows:

1. Physician's global assessment of disease activity
2. Participant's assessment of disease activity (Participant's overall well-being)
3. Functional ability assessed using Health Assessment Questionnaire (HAQ)
4. Number of active joints (68 joints evaluated for pain/tenderness and 66 for swelling)
5. Laboratory measure of inflammation: CRP (standardized) (mg/L)
6. Absence of intermittent fever in the preceding week

### **Corticosteroid dose tapering**

For oral corticosteroid dose, summary statistics for the change/percent change from baseline will be provided by scheduled visit after Week 8. The scheduled visits are defined as every 4 weeks through Week 48 and every 12 weeks thereafter.

The oral corticosteroid dose will be derived on prednisone equivalent dose per day (mg/day).

## **Rash**

Frequency table with the number and percentage of participants in absent/present and typical or/and atypical if present will be provided by scheduled visit.

## **DAS28-CRP**

Summary statistics for the observed values and the change/percent change from baseline will be provided by scheduled visit.

Frequency table with the number and percentage of participants in each category of DAS28-CRP (high disease activity, moderate disease activity, low disease activity, and remission) will be provided by scheduled visit.

Frequency table with the number and percentage of participants in each category of EULAR response criteria (based on DAS28-CRP) (good response, moderate response, and no response) will be provided by scheduled visit.

Details on how to categorize the DAS28-CRP and EULAR response criteria are given in [Section 5.6.2](#).

